3.2 Number of Sites

Approximately three sites globally will be utilized in this study. Additional sites may be added as necessary to complete enrollment.

3.3 Number of Subjects

Participants in this clinical investigation shall be referred to as "subjects".

A total of up to 61 migraine subjects are planned to be enrolled into the study. Up to 25 subjects may participate in Part A and up to 36 in Part B of the study. If ambiguous results in Part A occur regarding the ability of PACAP-38 ideally safely trigger a headache in all subjects within a given cohort (although, safely triggering headaches in the majority of subjects within a given cohort may be considered acceptable to advance to Part B of the study) and moderate to severe MLAs in the majority of subjects within the same cohort, then a previously dosed cohort sample size may be expanded to up to 5 subjects per cohort. Once the PACAP-38 dose has been selected, 8 subjects will be randomized to placebo and 8 subjects will be randomized to AMG 334. The data collected for the 16 Randomized (AMG 334 or Placebo) Subjects will be included in the interim analysis (See Section 10.4.1). Following the interim analysis, if the decision is to continue enrollment for the study, an additional 10 subjects will be randomized to AMG 334.

The sample size justification is described in Section 10.2.

3.4 Replacement of Subjects

Subjects who are withdrawn or removed from treatment or the study prior to receiving PACAP-38 will be replaced, at the discretion of the Amgen Medical Monitor and Principal Investigator by notifying the unblinded study pharmacist or designee. The new subject will receive the identical treatment as the replaced subject but will be assigned a replacement number associated with this new record. The unblinded study pharmacist or designee will retain the randomization list.

3.5 Estimated Study Duration

3.5.1 Study Duration for Subjects

For Part A: Non Randomized (PACAP-38 Only) Dose Selection Subjects, the planned length of participation in the study for an individual subject is approximately 29 days,

which includes the initial screening phase up to 3 weeks, 1 day of challenge agent administration, and 7 day safety follow-up.

For Part B: Randomized (AMG 334 or Placebo) Subjects, the planned length of participation in the study for an individual subject is approximately 106 days, which includes the initial screening phase up to 3 weeks, 1 day of treatment, 6 days to allow drug distribution, 1 day of challenge agent administration, and 11-week safety follow-up.

3.5.2 End of Study

See Section 3.5.1 for study duration for individual subjects.

Primary Completion: The time when the last subject is assessed or receives an intervention for the purposes of final collection of data for the primary analysis (ie, when the last subject completes the migraine questionnaire 24 hours after challenge agent administration or is discontinued from the study).

End of Trial: The time when the last subject is assessed or receives an intervention for evaluation in the study (ie, when the last subject completes the study, which includes the safety follow-up visit 11 weeks after the challenge agent administration, or is discontinued from the study).

4. SUBJECT ELIGIBILITY

Investigators will be expected to maintain a screening log of all potential study candidates that includes limited information about the potential candidate (eg, date of screening).

Before any study-specific activities/procedure, the appropriate written informed consent must be obtained (see Section 11.1).

4.1 Inclusion Criteria

To be eligible for the study, subjects must provide written informed consent to participate and must fulfill the following criteria:

- 4.1.1 Subject has provided informed consent prior to initiation of any study-specific activities/procedures
- 4.1.2 Adults \geq 18 to \leq 45 years of age upon entry into screening
- 4.1.3 History of migraine headaches without aura for ≥ 6 months prior to screening according to the IHS Classification ICHD-II (Headache Classification Committee of the International Headache Society, 2004) based on medical records and/or patient self-report
- 4.1.4 Migraine frequency: \geq 1 and \leq 5 migraine days per month in each of the 3 months prior to screening

- 4.1.5 Body mass index between 18 and 35 kg/m², inclusive at screening
- 4.1.6 No history or evidence of clinically relevant medical disorders as determined by the investigator in consultation with the Amgen physician
- 4.1.7 Physical, neurological, clinical laboratory values and ECGs are clinically acceptable to the investigator and Amgen

4.2 Exclusion Criteria

Subjects who fulfill any of the following criteria are not eligible for the study:

- 4.2.1 History of migraine with aura, cluster headache or hemiplegic migraine headache according to the IHS Classification ICHD-II (Headache Classification Committee of the International Headache Society, 2004) based on medical records and/or patient self-report
- 4.2.2 Greater than or equal to 6 migraine days per month in the last 3 months prior to study enrollment and during screening period
- 4.2.3 Other headache disorders (except for episodic tension-type headache <5 days/month)
- 4.2.4 Recent nicotine or tobacco users (should have stopped approximately 6 months prior to screening)
- 4.2.5 History or evidence of clinically significant disorder (including psychiatric), condition or disease that, in the opinion of the Investigator or Amgen physician would pose a risk to subject safety or interfere with the study evaluation, procedures, or completion
- 4.2.6 Pregnant or breastfeeding, or is a female expecting to conceive during the study, including through 12 weeks after the last dose of investigational product
- 4.2.7 Female subject of childbearing potential who is unwilling to use an acceptable method of effective contraception during treatment with investigational product through 12 weeks after the last dose of investigational product. Acceptable methods of effective birth control include not having intercourse (true abstinence, when this is in line with the preferred and usual lifestyle of the subject), hormonal birth control methods (pills, shots/injections, implants, or patches), intrauterine devices, surgical contraceptive methods (vasectomy with medical assessment of the surgical success of this procedure or bilateral tubal ligation), or two barrier methods (each partner must use one barrier method) with spermicide males must use a condom with spermicide; females must choose either a diaphragm with spermicide. Female subjects not of childbearing potential are defined as any female who:
 - Is post-menopausal by history, defined as:
 - Age ≥ 55 years with cessation of menses for 12 or more months, OR
 - Age < 55 years but no spontaneous menses for at least 2 years, OR

 Age < 55 years and spontaneous menses within the past 1 year, but currently amenorrheic (eg, spontaneous or secondary to hysterectomy), AND with postmenopausal gonadotropin levels (luteinizing hormone and follicle-stimulating hormone levels > 40 IU/L) or postmenopausal estradiol levels (< 5 ng/dL) or according to the definition of "postmenopausal range" for the laboratory involved.

OR

- Underwent bilateral oophorectomy OR
- Underwent hysterectomy OR
- Underwent bilateral salpingectomy
- 4.2.8 A history of hypertension, hypotension, myocardial ischemia, angina, palpitations, flushing, tachydysrythmias (eg, atrial fibrillation), coronary artery bypass surgery, stroke, or transient ischemic attack, coronary artery disease with or without angina pectoris, percutaneous angioplasty procedure, any cerebrovascular events included but not limited to Cerebral Vascular Accident and Transient Ischemic Attack, Peripheral Vascular Disease
- 4.2.9 A baseline systolic BP \geq 135 mmHg / diastolic BP \geq 85 mmHg
- 4.2.10 A baseline ECG $QTc \ge 450$ ms
- 4.2.11 A baseline heart rate >85 beats/min
- 4.2.12 Estimated glomerular filtration rate (eGFR) within the screening period of less than 60 mL/min/1.73m² as calculated using the estimated Modification of Diet in Renal Disease (MDRD) formula
- 4.2.13 Subjects with Hemoglobin A1C > 6% at screening
- 4.2.14 Positive for HIV antibodies, hepatitis B surface antigen, positive hepatitis core antibody, or hepatitis C antibodies at screening
- 4.2.15 A history of malignancy of any type, other than surgically excised non-melanomatous skin cancers or in situ cervical cancer within 5 years before the day of dosing
- 4.2.16 Has donated or lost 500 mL or more of blood or plasma within 8 weeks of Day 1 or has a history of chronic anemia
- 4.2.17 Subject previously has entered this study or has been previously exposed to AMG 334 or PACAP-38
- 4.2.18 History of hypersensitivity or allergic reaction to PACAP-38, CGRP receptor antagonist and any components to be administered during the study
- 4.2.19 Receiving or has received any investigational drug (or is currently using an investigational drug or device) within 30 days or 5 half-lives (whichever is longer), prior to receiving the first dose of AMG 334
- 4.2.20 Treatment with any biologic agent (such as monoclonal antibodies) within 3 months or 5 half-lives (whichever is greater) prior to dosing or have received a vaccination within 1 month prior to dosing

4.2.21	Use of any over-the-counter or prescription medications (specifically
	including, but not limited to triptans, ergotamine & topiramate) within the
	14 days or 5 half-lives (whichever is longer), prior to receiving the first dose of
	AMG 334. Paracetamol (up to 2 g per day) for analgesia and hormone
	replacement therapy (eg, estrogen, thyroid) will be allowed. Simple
	analgesics including NSAIDs will be allowed, but not within 48 hours prior
	infusion of PACAP38. Any preventive medication is contra-indicated

- 4.2.22 Any herbal medicines (eg, St. John's wort), vitamins, and supplements consumed by the subject within 21 days prior to receiving the first dose of AMG 334, and continuing use if applicable, will be reviewed by the PI and the Amgen Medical Monitor. Written documentation of this review and Amgen acknowledgement are required for subject participation
- 4.2.23 Prior or current history of psychiatric illness, such as anxiety, depression, or schizophrenia
- 4.2.24 History of suicidal behavior and/or ongoing suicidal ideation as assessed using the Columbia Suicide Severity Rating Scale (C-SSRS)
- 4.2.25 Known substance abuse (eg, alcohol, illicit or illegal drugs) within 1 year of dosing
- 4.2.26 Positive test for drug, cotinine or alcohol use at screening
- 4.2.27 Inability or unwillingness to refrain from alcohol consumption 24 hours prior to study visits
- 4.2.28 Subject unwilling to refrain from strenuous exercise during screening, in-clinic visits, and the outpatient visits
- 4.2.29 Subject will not be available for protocol-required study visits or procedures, to the best of the subject and investigator's knowledge
- 4.2.30 Subject has any kind of disorder that, in the opinion of the investigator, may compromise the ability of the subject to give written informed consent and/or to comply with all required study procedures
- 4.2.31 Troponin I or Troponin T at screening > upper limit of normal (ULN)

5. SUBJECT ENROLLMENT

Before subjects begin participation in any study-specific activities/procedures, Amgen requires a copy of the site's written institutional review board/independent ethics committee (IRB/IEC) approval of the protocol, informed consent form (ICF), and all other subject information and/or recruitment material, if applicable (see Section 11.2). All subjects must personally sign and date the IRB/IEC approved informed consent form before commencement of study-specific procedures. Adverse Events are to be collected for a subject once they are enrolled in the study.

A subject is considered enrolled when the investigator decides that the subject has met all eligibility criteria. The investigator is to document this decision and date, in the subject's medical record and in/on the enrollment eCRF page.

Provided all eligibility criteria have been met, all eligible subjects will be enrolled on Day 1. Following Part A: PACAP-38 Dose Selection Phase, a minimum of 16 and a maximum of 36 Randomized (AMG 334 or Placebo) Subjects in Part B will be randomized on Day 1 (day of investigational product administration) to receive either AMG 334 or matching placebo in a one to one allocation ratio.

Each subject who enters into the screening period for the study (Day -21 to Day -1) receives a unique subject identification number before any study procedures are performed. The subject identification number will be assigned manually. This number will be used to identify the subject throughout the clinical study and must be used on all study documentation related to that subject.

Screen failed subjects may be rescreened at the discretion of the PI with agreement from the MM.

The subject identification number must remain constant throughout the entire clinical study; it must not be changed after initial assignment, including if a subject is rescreened. This number will not necessarily be the same as the randomization number assigned for the study.

5.1 Randomization/Treatment Assignment

Section 5.1 does not apply to Part A: Non Randomized (PACAP-38 Only) Dose Selection Subjects.

For Randomized (AMG 334 or Placebo) Subjects in Part B, randomization to AMG 334 or matching placebo will be based on a randomization schedule prepared by Amgen before the start of the study. Eligible subjects must be randomized on Day 1 during which time they will be receiving a unique randomization number and assigned to receive either AMG 334 or matching placebo. Once eligibility for study participation has been confirmed (based on data collected during screening visit and on Day -1), a randomization number will be assigned in sequential order in which eligibility was met. At no time will the same randomization number be assigned to more than one subject.

In the event a subject is randomized, but withdraws before receiving study medication, or during the study for reasons other than adverse events (Section 9.1), a replacement subject may be enrolled at the discretion of the Amgen Medical Monitor and Principal Investigator by notifying the unblinded study pharmacist or designee. The new subject will receive the identical treatment as the replaced subject but will be assigned a replacement number associated with this new record. The unblinded study pharmacist or designee will retain the randomization list.

The randomization date is to be documented in the subject's medical record and on the enrollment eCRF.

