The sponsor is the exclusive owner of any data, discoveries, or derivative materials from the sample materials and is responsible for the destruction of the sample(s) at the request of the subject through the investigator, at the end of the storage period, or as appropriate (eg, the scientific rationale for experimentation with a certain sample type no longer justifies keeping the sample). If a commercial product is developed from this research project, the sponsor owns the commercial product. The subject has no commercial rights to such product and has no commercial rights to the data, information, discoveries, or derivative materials gained or produced from the sample. See Section 11.3 for subject confidentiality.

8. WITHDRAWAL FROM TREATMENT, PROCEDURES, AND STUDY 8.1 Subjects' Decision to Withdraw

Subjects have the right to withdraw from the study at any time and for any reason without prejudice to their future medical care by the physician or at the institution.

Withdrawal of consent for a study means that the subject does not wish to receive further protocol-required therapies or procedures, and the subject does not wish to or is unable to continue further study participation. Subject data up to withdrawal of consent will be included in the analysis of the study, and where permitted, publically available data can be included after withdrawal of consent. The investigator is to discuss with the subject appropriate procedures for withdrawal from the study.

8.2 Investigator or Sponsor Decision to Withdraw or Terminate Subjects' Participation Prior to Study Completion

The investigator and/or sponsor can decide to withdraw a subject(s) from investigational product and/or other protocol required therapies, protocol procedures, or the study as a whole at any time prior to study completion.

Subjects may be eligible for continued treatment with Amgen investigational product(s) and/or other protocol required therapies by a separate protocol or as provided for by the local country's regulatory mechanism, based on parameters consistent with Section 12.1.

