10. STATISTICAL CONSIDERATIONS

- 10.1 Study Endpoints, Analysis Sets, and Covariates
- 10.1.1 Study Endpoints
- 10.1.1.1 Primary Endpoint
 - Occurrence of a migraine-like attack within 24 hours of challenge-agent infusion

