10.3 Access to Individual Subject Treatment Assignments by Amgen or Designees

Blinded individuals will not have access to unblinded information until the study is formally unblinded. Unblinding and potentially unblinding information should not be distributed to the study team, investigators or subjects prior to the study being formally unblinded (eg, the formal unblinding may occur at the final analysis rather than during the primary analysis) except as specified (eg, Section 5.2 and Section 9.2.2.2).

Unless otherwise specified in this section, subjects, site personnel, or Amgen staff and their designees will not have access to unblinding information until the study is formally unblinded. Unblinded individuals, as designated in this section, are to ensure unblinding information and potentially unblinding data are not distributed to blinded individuals until the study is formally unblinded.

A subject's treatment assignment should only be unblinded when knowledge of the treatment is essential for the further management of the subject on this study or may potentially impact the safety of subjects currently enrolled. Unblinding at the study site for any other reason will be considered a protocol deviation. The investigator is strongly encouraged to contact the Amgen clinical study manager before unblinding any subject's treatment assignment, but must do so within 1 working day after the event and must document the unblinding in the subject's eCRF.

Individual subject treatment assignments will be unblinded to personnel from Pharmacokinetics and Drug Metabolism, Clinical Immunology, Biological Sample Management, and Molecular Sciences & Computational Biology departments associated with tracking, assaying, and analyzing the PK samples, biomarker development samples. Furthermore, individual subject treatment assignments will be unblinded to designated personnel from Biostatistics at 2 timepoints during the study: 1) the interim analysis (personnel from Biostatistics performing the interim analysis only), and 2) after formal unblinding (see below). Access to individual subject data will be limited to unblinded staff until the official unblinding occurs. Prior to unblinding, when knowledge of the treatment assignment is essential for the further management of the subject or potentially affects the safety of subjects, the randomization code may be broken.

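### Protocol sections 3.4 and 5.1 conflict on replacement in Part B, and 5.1 as written lets a same-arm subject be added after the primary outcome is known

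*Protocol*

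**What the plan says.** Protocol section 3.4: "Subjects who are withdrawn or removed from treatment or the study prior to receiving PACAP-38 will be replaced", at the discretion of the Medical Monitor and the Principal Investigator. It has no exception for adverse events.

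Protocol section 5.1, which applies to Part B only, covers a randomised subject who withdraws before study medication, "or during the study for reasons other than adverse events". In that case "a replacement subject may be enrolled at the discretion of the Amgen Medical Monitor and Principal Investigator", and "The new subject will receive the identical treatment as the replaced subject". It sets no limit tied to the challenge.

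The primary endpoint (section 10.1.1.1) is "Occurrence of a migraine-like attack within 24 hours of challenge-agent infusion". Section 3.5.1 then lists "1 day of challenge agent administration, and 11-week safety follow-up".

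On who is analysed, section 8.1 says: "Subject data up to withdrawal of consent will be included in the analysis of the study". The protocol's safety analysis set (10.1.2.1) is everyone given investigational product (IP) and PACAP-38. Section 10.5.1 of the protocol and section 11 of the SAP leave out of the summaries only subjects who received IP but not PACAP-38. The SAP has no replacement rule.

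The interim analysis (Protocol 10.4.1, SAP 8.2) uses 8 subjects per group, and a trial that continues ends with 18 per group. Rule 1 stops the trial for assay failure when three or fewer of the eight placebo subjects have a migraine-like attack (MLA).

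**The concern.** The two sections cannot both govern. They disagree on whether a subject who has had the challenge can be replaced. They also disagree on whether a subject who leaves for an adverse event between IP and PACAP-38 can be replaced: 3.4 allows it and 5.1 does not.

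The first disagreement matters more. Under 5.1, a subject challenged on Day 8 who withdraws during follow-up for a reason other than an adverse event can be followed by a new subject on the same arm. By then the primary outcome is known at the site: staff record the headache questionnaire (7.2.12), and MLAs also go on the adverse event page (9.2.2.1). The decision is discretionary, so it can be influenced by that outcome.

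The first subject's outcome stays in the data, so the arm gains an outcome. The plan does not say whether the original, the replacement or both belong to the 8 or the 18. Nor does it say how a threshold written for 8 placebo subjects applies to 9. Rule 1 is the most exposed, because it alone is an absolute count out of a named 8. Rule 2 compares counts between arms, rule 3 is a difference in proportions, and the final Fisher's exact test does not need equal groups.

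**Working it through.** **Inputs.** From Protocol 10.4.1: 8 per arm at the interim, then 10 more per arm; rules 1 to 3; final one-sided Fisher's exact test at p < 0.1. Placebo MLA rates: 70% (planning, 10.2), about 66% (historical, 10.4.1) and 50% (a scenario in the 10.4.1 tables). AMG 334 rate: 20% (10.2).

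**Assumptions, because the documents give no withdrawal or replacement rate.** One addition happens before the interim, it follows a subject without an MLA, and the threshold of 3 is applied unchanged.

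**1. The plan's own figures.** Exact enumeration of the two-stage design gives these results:

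| Placebo / AMG 334 rate | Quantity | Plan | Exact |
|---|---|---|---|
| 70% / 20% | success | 91% | 90.95% |
| 70% / 20% | interim failure | 6% | 6.0% |
| 70% / 70% | success (false) | 5% | 5.2% |
| 50% / 50% | success (false) | 6% | 6.2% |

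The plan's figures reproduce. They assume exactly 8 + 10 per arm and no replacement that depends on outcome.

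**2. Assay-failure stop with no addition.** With X the placebo MLA count, X ~ Binomial(8, p). P(X ≤ 3) = 0.36328, 0.09494 and 0.05797, and P(X = 3) = 0.21875, 0.07315 and 0.04668, at p = 0.50, 0.66 and 0.70.

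**3. Worst case: the subject was on placebo.** A subject without an MLA contributes zero to the count, so keeping that subject and adding one new draw changes the decision only when X = 3 and the new subject has an MLA. The stop probability becomes P(X ≤ 3) − p × P(X = 3):

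- p = 0.50: 0.36328 − 0.50 × 0.21875 = 0.2539
- p = 0.66: 0.09494 − 0.66 × 0.07315 = 0.0467
- p = 0.70: 0.05797 − 0.70 × 0.04668 = 0.0253

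**4. Blinded pick of one non-MLA subject from either arm.** When X = 3 there are 5 non-MLA subjects on placebo and 8 − Y on AMG 334, with Y ~ Binomial(8, 0.20). The chance that the pick falls on placebo averages w = E[5 / (13 − Y)] = 0.4433. The stop probability becomes P(X ≤ 3) − w × p × P(X = 3):

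- p = 0.50: 0.36328 − 0.4433 × 0.50 × 0.21875 = 0.3148
- p = 0.66: 0.09494 − 0.4433 × 0.66 × 0.07315 = 0.0735
- p = 0.70: 0.05797 − 0.4433 × 0.70 × 0.04668 = 0.0435

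| Placebo rate | No addition | Blinded pick | Worst case |
|---|---|---|---|
| 50% | 36.3% | 31.5% | 25.4% |
| 66% | 9.5% | 7.4% | 4.7% |
| 70% | 5.8% | 4.3% | 2.5% |

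If AMG 334 has no effect, so both arms share the placebo rate, the blinded-pick figures are 30.1%, 6.3% and 3.5%.

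**5. False success with the original kept.** Adding one or two placebo subjects at the interim stage, each after a non-MLA outcome, gives 5.0–5.1% at 70%/70% and 4.9–6.2% at 50%/50%. Without additions the figures are 5.2% and 6.2%.

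**The case against.** The analysis rules already limit the damage, and this part of the objection stands. A challenged subject is never removed from the count, so one outcome cannot be exchanged for another. The deciders are two people, and section 10.3 says that site and sponsor staff, with named exceptions, "will not have access to unblinding information until the study is formally unblinded". The unblinded pharmacist is notified but does not decide.

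The event may also be rare, and that stands too. A challenged subject must withdraw for a reason other than an adverse event. The replacement must then be screened, dosed and challenged a week later, all before the interim. Section 3.1 ties the interim to the first 16 challenged subjects, so many late withdrawals could not affect it.

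A reader might infer that 5.1 lets the sponsor swap unfavourable outcomes and inflate the type I error. The documents do not support that. If originals were dropped but the deciders stayed blinded, with one or two non-MLA subjects per arm redrawn in both stages, false success would be 6.8–7.0% (70%/70%) and 7.4–8.3% (50%/50%), below the 10% test level. Higher figures need the original dropped and the arm known: 10.9% and 12.4% with one subject per arm at the first stage, and about 20% with one per arm in both stages. The plan provides for neither condition.

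Blinding does not settle the matter for rule 1. Adding a subject after a non-MLA outcome can never lower the placebo count, and it raises that count when the addition falls on placebo and has an MLA. No section reconciles 3.4 with 5.1.

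**Conclusion.** The contradiction is real and worth correcting. Followed as written, section 5.1 permits an outcome-aware addition to one arm, and the plan does not define who forms the 8 and the 18.

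The size is modest and conditional on one addition before the interim with the threshold of 3 unchanged. At the planning rate of 70% the assay-failure stop falls from 5.8% to 4.3% with a blinded pick, or to 2.5% at worst. At 66% it falls from 9.5% to 7.4% or 4.7%. The largest change is at a 50% placebo rate, which is below both the planning and the historical rates. The effect is that more trials pass the assay check; false success stays near 5–6% with originals kept. This is a matter of integrity and clarity, not a demonstrated failure of error control.

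One caveat: the protocol reviewed is dated 01 September 2016 (Amendment 3), while the SAP implements Amendment 4 of 21 October 2016. Whether Amendment 4 kept the wording of 5.1 cannot be seen.

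**What to change.** - Delete "or during the study for reasons other than adverse events" from section 5.1.
- Use one rule in 3.4 and 5.1: replace only randomised subjects who do not receive PACAP-38, whatever the reason. This also settles the adverse-event disagreement.
- State in the protocol and the SAP that every subject given IP and PACAP-38 counts in the primary analysis and in the interim rules, and is not replaced. The 8 and 18 per group are then defined by challenged subjects.
- In the SAP's design, PACAP-38-naïve subjects also receive PACAP-38 before randomisation, so the rule should name the challenge given after IP.

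The cost is a few sentences of wording. Subjects who withdraw after the 24-hour assessment would not be replaced, which loses only follow-up safety, pharmacokinetic and antibody data. If Amendment 4 already contains such a rule, only the SAP statement remains to be added.
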